## **8.6. Efficacy Analysis**

### **8.6.1. Primary Efficacy Endpoints Analysis**

#### **Primary Histology Efficacy Endpoint Analysis**

A stratified MH test will be used to compare the differences in proportions of subjects who achieve a  $\geq 1$ -stage improvement in fibrosis without worsening of NASH at Week 48 between each of the SEL arms and the placebo arm, adjusting for stratification factors. Subjects with missing data regarding fibrosis stage and NAS elements used to define worsening of NASH (hepatocellular ballooning and lobular inflammation) at Week 48 will be analyzed as treatment failures. The point estimates and 95% confidence intervals for the differences in proportions will be calculated.

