1.3. Sample Size and Power

With a sample size of 320 subjects in each active treatment arm and 160 subjects in the placebo arm, the study has 94% power to detect a difference in the proportion of subjects with a ≥ 1 -stage improvement in fibrosis without worsening of NASH of 15% or more at Week 48 at a significance level of 0.025 (2-sided), assuming the proportion of subjects that meet the endpoint in the placebo arm is 12%.

With regard to the clinical efficacy endpoint, subjects will be followed for a period of up to 240 weeks. The estimate of the expected event rate is 30% in untreated patients, producing an expected EFS rate of 70% at 240 weeks in the placebo arm. SEL is expected to improve the EFS rate to 83.7% (expected event rate of 16.3%) compared with placebo (hazard ratio (HR), 0.50). We also expect a 20% overall dropout rate. Given the above assumptions, for comparison of the SEL arms versus the placebo arm, together with a total sample size of 800 subjects (2:2:1 ratio), and assuming the log-rank test statistic is evaluated using a 2-sided 0.025 significance level, the study will have 85% power to evaluate the superiority of each SEL arm versus placebo with respect to EFS.

Therefore, the overall power for the trial, assuming independence between the primary efficacy endpoint and clinical efficacy endpoint, is 80% ($94\% \times 85\%$). It should be noted that this is a lower bound estimate as these 2 endpoints are expected to be positively correlated.

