3.5. Multiple Testing

[figure not shown]
When the primary histology efficacy endpoint is compared between each of the SEL arms and the placebo arm at Week 48, it will be tested at a 2-sided 0.025 significance level to control for an overall Type I error rate of 0.05 by Bonferroni adjustment.

The testing strategy for the clinical efficacy endpoint (EFS) is described below and is presented graphically in [Figure 3-1](#).

- 1) If the primary histology efficacy endpoint is significant in both SEL arms, the EFS endpoint will be tested for both SEL arms against placebo at Week 240 at a 2-sided 0.05 significance level by the Hochberg procedure {[Hochberg 1988](#)}. If the larger p-value of SEL18 mg versus placebo and SEL 6 mg versus placebo is less than or equal to 0.05, the EFS endpoint for both SEL arms will be a success; if the larger p-value is > 0.05 , the treatment arm with the larger p-value fails, and the smaller p-value will be compared with the significance level of 0.025 to determine the success of the treatment arm.

- 2) If the primary histology efficacy endpoint is significant in the SEL 18 mg arm but not the SEL 6 mg arm, the EFS endpoint will be tested for SEL 18 mg against placebo at Week 240 at a 2-sided 0.025 significance level.
- 3) If the primary histology efficacy endpoint is significant in the SEL 6 mg arm but not the SEL 18 mg arm, the EFS endpoint will be tested for SEL 6 mg against placebo at Week 240 at a 2-sided 0.025 significance level.
- 4) If the primary histology efficacy endpoint is not significant in either the SEL 18 mg or SEL 6 mg arms, the trial will be terminated.

Figure 3-1. Multiple Testing Flow Chart

* Nominal alpha will be adjusted using the Haybittle-Peto approach

Although no formal statistical inference on EFS is planned for the Week 48 Interim Analysis, the actual nominal significance level for the EFS endpoint at the Week 240 Analysis will be adjusted using the Haybittle-Peto approach {[Haybittle 1971](#)}. The adjustment will be based on the number of events at both the Week 48 and Week 240 analyses, assuming an allocation of a 2-sided significance level of 0.001 at the Week 48 Interim Analysis.

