6.1.2. Statistical Hypothesis for Primary Histology Efficacy Endpoint

The statistical hypotheses to be tested can be stated as:

$$H_{S0i}: \delta_{si} = 0 \text{ versus } H_{SAi}: \delta_{si} \neq 0, i = 1 \text{ or } 2$$

Where δ_{s1} (δ_{s2}) is the difference in the proportion of subjects who achieve a ≥ 1 -stage improvement in fibrosis without worsening of NASH at Week 48 between SEL 18 mg (or SEL 6 mg) and placebo. The hypotheses will be tested in the FAS with $\alpha = 0.025$ for the comparison between each SEL arm and the placebo arm. The study will evaluate if each SEL arm performs better (ie, has a higher proportion of subjects who achieve a ≥ 1 -stage improvement in fibrosis without worsening of NASH) than the placebo arm.

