6.1.3. Analysis of Primary Histology Efficacy Endpoint

A stratified Mantel-Haenszel (MH) test will be used to compare the differences in proportions of subjects who achieve a ≥ 1 -stage improvement in fibrosis without worsening of NASH at Week 48 between SEL 18 mg (SEL 6 mg) and placebo, adjusting for the presence or absence of diabetes mellitus at baseline and ELF test score ≥ 9.76 or < 9.76 at baseline. Subjects with missing data regarding fibrosis stage and NAS elements used to define worsening of NASH (hepatocellular ballooning and lobular inflammation) at Week 48 will be analyzed as treatment failures for this endpoint. The 2-sided 95% CIs for the difference in proportions between SEL 18 mg (SEL 6 mg) and placebo will be constructed based on stratum-adjusted MH proportions as follows {Koch 1989}:

$$p_A - p_B \pm Z_{(1-\alpha/2)} * SE(p_A - p_B),$$

where

- $(p_A - p_B) = \frac{\sum w_h d_h}{\sum w_h}$, is the stratum-adjusted MH proportion difference, where $d_h = p_{Ah} - p_{Bh}$ is the difference in the proportion of subjects who achieved a ≥ 1 -stage improvement in fibrosis without worsening of NASH between SEL 18 mg (SEL 6 mg) and placebo in stratum h.

- $w_h = \frac{n_{Ah}n_{Bh}}{n_{Ah} + n_{Bh}}$, is the weight based on the harmonic mean of sample size per treatment group for each stratum where n_{Ah} and n_{Bh} are the sample sizes of SEL 18 mg (SEL 6 mg) and placebo in stratum h.

- $SE(p_A - p_B) = \sqrt{\frac{\sum w_h^2 \left[\frac{p_{Ah}^*(1-p_{Ah}^*)}{n_{Ah}-1} + \frac{p_{Bh}^*(1-p_{Bh}^*)}{n_{Bh}-1} \right]}{(\sum w_h)^2}}$, where

$$p_{Ah}^* = \frac{m_{Ah} + 0.5}{n_{Ah} + 1} \text{ and } p_{Bh}^* = \frac{m_{Bh} + 0.5}{n_{Bh} + 1}, \text{ and}$$

m_{Ah} and m_{Bh} are the number of subjects who achieved a ≥ 1 -stage improvement in fibrosis without worsening of NASH in SEL 18 mg (SEL 6 mg) and placebo in stratum h.

- $\alpha = 0.05$ for the calculation of 95% CI
- $Z_{(1-\alpha/2)} = Z_{0.975} = 1.96$ is the 97.5th percentile of the normal distribution
- $Z \text{ score} = \frac{(p_A - p_B)}{SE(p_A - p_B)}$

If the computed lower confidence bound is less than -1 , the lower bound is defined as -1 . If the computed upper confidence bound is greater than 1 , then the upper bound is defined as 1 .

The point estimates, 95% CIs, and corresponding p-values based on Z tests for the differences in proportions, and the 95% CIs for proportion of responders in each treatment group based on the Clopper-Pearson method will be calculated.

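### The two primary histology differences are tested at two-sided 0.025 but reported with 95% confidence intervals, so an interval can exclude zero for an arm that failed its test

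*SAP*

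**What the plan says.** **The test.** SAP 3.5 says of each dose-placebo comparison at Week 48 that "it will be tested at a 2-sided 0.025 significance level to control for an overall Type I error rate of 0.05 by Bonferroni adjustment". SAP 6.1.2 repeats the level: "The hypotheses will be tested in the FAS with $\alpha = 0.025$ for the comparison between each SEL arm and the placebo arm". Protocol 8.4 agrees. Under the same sections, an arm goes forward to EFS testing only if it passes at this level, and the trial stops if neither arm passes.

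**The interval.** SAP 6.1.3 states: "The 2-sided 95% CIs for the difference in proportions between SEL 18 mg (SEL 6 mg) and placebo will be constructed". It sets alpha to 0.05 for that purpose and gives the multiplier as 1.96, which "is the 97.5th percentile of the normal distribution"; this is the ordinary quantile for a 95% interval, not a 97.5% interval. Protocol 8.6.1 says: "The point estimates and 95% confidence intervals for the differences in proportions will be calculated". The protocol synopsis has the same provision.

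**What is reported together.** SAP 6.1.3 lists "The point estimates, 95% CIs, and corresponding p-values based on Z tests for the differences in proportions" as one set of outputs. The Z score there is the stratum-adjusted difference divided by the same standard error that enters the interval.

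Neither document plans a 97.5% interval for this endpoint, and neither labels the 95% intervals as unadjusted or descriptive.

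**The concern.** A reader normally takes an interval that excludes zero to mean that the comparison reached significance. Here that holds only at 0.05, while the plan declares success at 0.025. The multiplicity adjustment was applied to the test but not to the estimate printed beside it.

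The primary results table could then show an interval wholly above zero for a dose that the testing plan counts as a failure. This would happen at the analysis that decides which dose proceeds to EFS and whether the trial goes on. The risk is one of interpretation: a study report or publication could present the failed dose as having shown benefit, with the plan's own interval as support.

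**Working it through.** **Inputs.** From SAP 1.3: 320 per active arm, 160 on placebo, placebo response 12%, design difference 15 points (so 27% on active), two-sided 0.025. From SAP 6.1.3: the standard error and Z formulas.

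**1. The plan's own figure.** SAP 1.3 states: "With a sample size of 320 subjects in each active treatment arm and 160 subjects in the placebo arm, the study has 94% power". The pooled rate is (160 × 0.12 + 320 × 0.27)/480 = 0.22.

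- Null SE = √(0.22 × 0.78 × (1/160 + 1/320)) = 0.0401.
- Alternative SE = √(0.12 × 0.88/160 + 0.27 × 0.73/320) = 0.0357.
- Power = Φ((0.15 − 2.241 × 0.0401)/0.0357) = 95.4%; with a continuity correction of 0.0047 it is 94.0%.
- With 1.960 in place of 2.241 the uncorrected figure is 97.7%.

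The stated 94% is reproduced at 0.025, so the design uses the critical value 2.241.

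**2. Critical values.** z(0.9875) = 2.241 for the test and z(0.975) = 1.960 for the interval. Their ratio is 1.144. Every result with 1.960 < |Z| < 2.241 is discordant.

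**3. A worked case.** Take placebo 19/160 and SEL 61/320 in a single stratum, with the SAP 6.1.3 formula.

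- Difference = 0.1906 − 0.1188 = 0.0719.
- Adjusted rates: (61 + 0.5)/321 = 0.1916 and (19 + 0.5)/161 = 0.1211.
- SE = √(0.1916 × 0.8084/319 + 0.1211 × 0.8789/159) = 0.0340.
- Z = 0.0719/0.0340 = 2.115; p = 0.0344, so the test fails.
- 95% interval: 0.5 to 13.9 points. 97.5% interval: −0.4 to 14.8 points.

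Neighbouring counts, with placebo held at 19/160:

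| SEL responders of 320 | Z | p | 95% lower bound (points) | 97.5% lower bound (points) |
|---|---|---|---|---|
| 59 | 1.941 | 0.0522 | −0.06 | −1.01 |
| 60 | 2.028 | 0.0425 | +0.23 | −0.72 |
| 61 | 2.115 | 0.0344 | +0.53 | −0.43 |
| 62 | 2.201 | 0.0277 | +0.82 | −0.14 |
| 63 | 2.287 | 0.0222 | +1.12 | +0.16 |

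The 95% interval contradicts the test at 60, 61 and 62 responders. The 97.5% interval agrees with the test in every row.

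**4. How often, per arm.** With true rate p_T on active, SE = √(0.12 × 0.88/160 + p_T(1 − p_T)/320) and m = (p_T − 0.12)/SE. The chance of a discordant result in favour of SEL is Φ(2.241 − m) − Φ(1.960 − m).

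| True SEL rate (difference) | Chance per arm |
|---|---|
| 12% (0) | 1.25% (2.5% counting both directions) |
| 17% (5 points) | 9.4% |
| 20% (8 points) | 10.9% |
| 22% (10 points) | 8.2% |
| 27% (15 points, design) | 1.3% |

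Simulation with the stratified SAP estimator agrees: 9.0%, 10.8%, 8.6% and 1.8% at 5, 7, 10 and 15 points. It assumes 70% of subjects diabetic and 50% with high ELF.

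**5. How often, at least one of the two arms.** The same simulation, with both doses given the same true effect, gives about 17%, 20%, 16% and 3% at 5, 7, 10 and 15 points. Cases where neither arm passes, so that the trial stops, and yet an interval lies above zero are about 11%, 11%, 6 to 7% and 0.7%.

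**The case against.** The strongest reply is that no decision uses the interval. SAP 3.5, SAP 6.1.2 and Protocol 8.4 define success, entry to EFS testing and termination by the test at 0.025 alone. That stands in full. A reader might infer from the mismatch that the type I error is inflated, or that a dose could be declared successful on its interval. The documents do not support either reading.

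It can also be said that the plan does not contradict itself: SAP 6.1.3 assigns alpha = 0.05 to the interval explicitly, and the p-value is printed beside it. Unadjusted 95% intervals next to adjusted tests are a common convention. This stands as a description of the plan. But the convention relies on labelling, and there is none here.

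Three further inferences go too far.

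- **Joint coverage.** Under a bivariate normal with correlation (1/160)/(1/160 + 1/320) = 2/3, the two 95% intervals jointly cover with probability 91.5%, against 95.6% for 97.5% intervals. Neither document promises simultaneous coverage, so 91.5% is not a breach of anything stated.
- **Forest plots.** SAP 6.1.3 plans them for subgroup and sensitivity analyses. It does not mention a row for the primary result.
- **Frequency.** The 17 to 20% figures count either arm at assumed effects of 5 and 7 points. They do not describe a single comparison, nor the effect for which the trial was sized.

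**Conclusion.** The point holds as a mismatch between the reported interval and the test. For any p between 0.025 and 0.05, the primary result will show a 95% interval excluding zero for a comparison that the plan calls a failure. Error control, power and the go/no-go rule are intact.

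The size depends on the true effect. It is about 8 to 11% per arm at true differences of 5 to 10 points (15 to 20% for at least one arm). At the design difference of 15 points it is under 2% per arm and about 3% for at least one arm. The 5 to 10 point differences, the strata mix and the equal effect in both doses are assumptions made to show a range. The worked case ignores stratification. The discordant zone itself, 1.960 < |Z| < 2.241, follows from the documents without any assumption.

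This is a modest reporting point. It is worth acting on because the remedy is nearly free and the analysis concerned is the trial's primary one.

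**What to change.** In SAP 6.1.3 set alpha = 0.025 and Z = 2.241 in the interval formula for the two primary SEL-placebo differences, and report 97.5% intervals. Make the matching change in Protocol 8.6.1 and the synopsis. SAP 6.3.2 borrows its method from 6.1.3 for the secondary endpoints, so the wording should confine the new level to the two primary comparisons.

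If 95% intervals are also shown, including in the subgroup and sensitivity forest plots and for the odds ratios, label them as unadjusted for multiplicity. State that significance for the primary endpoint rests on p against 0.025.

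**Cost.** Wording only, with no change to data collection, sample size or decision rule. The primary intervals become 14% wider (2.241/1.960 = 1.144). At the design rates the half-width goes from 1.960 × 0.0357 = 7.0 points to 2.241 × 0.0357 = 8.0 points.

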6.2. Clinical Efficacy Endpoint

6.2.1. Definition of Clinical Efficacy Endpoint

A composite of clinical events that constitute the clinical efficacy endpoint include:

1. Progression to cirrhosis as defined by a liver biopsy showing F4 fibrosis according to the NASH CRN classification as assessed by the central reader
2. Events of hepatic decompensation, including:
 - a) Clinically apparent ascites requiring treatment
 - b) Hepatic encephalopathy (HE) of Grade 2 or above (according to the West Haven criteria defined in Appendix 5 of the protocol) requiring treatment
 - c) Portal hypertension-related upper gastrointestinal bleeding identified by endoscopy and requiring hospitalization, including events of bleeding from esophageal varices, gastric varices, and portal hypertensive gastropathy
3. Liver transplantation or qualification for liver transplantation (defined as MELD score ≥ 15 on at least 2 consecutive occasions at least 4 weeks apart)
4. All-cause mortality

Each of these clinical events (except histologic progression to cirrhosis, all-cause mortality and liver transplantation) will require confirmation by a Hepatic Events Adjudication Committee. The onset date of the first clinical event (biopsy showing F4 fibrosis, death, liver transplantation or adjudication confirmed event) will be used in the analysis.

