**Randomized Study Phase**

Randomization will be stratified by the presence or absence of diabetes mellitus (as determined by medical history or based on Screening lab values if previously undiagnosed [i.e. hemoglobin A1c (HbA1c)  $\geq$  6.5% or fasting plasma glucose  $\geq$  126 milligram/deciliter [mg/dL]) and by Enhanced Liver Fibrosis (ELF™) score  $\geq$  9.76 or  $<$  9.76 during Screening. Study drugs will be administered for up to a total of 240 weeks.

A key primary objective of this study is to prevent progression to cirrhosis and its complications. A composite of clinical events that constitute the clinical efficacy endpoint have been identified and include:

- 1) Progression to cirrhosis as defined by a liver biopsy showing F4 fibrosis according to the NASH Clinical Research Network (CRN) classification as assessed by the central reader
- 2) Events of hepatic decompensation including:
  - a) Clinically apparent ascites requiring treatment
  - b) Hepatic encephalopathy (HE) of Grade 2 or above (according to the West Haven criteria as defined in [Appendix 5](#)) requiring treatment

- c) Portal hypertension-related upper gastrointestinal bleeding identified by endoscopy and requiring hospitalization, including events of bleeding from esophageal varices, gastric varices, and portal hypertensive gastropathy
- 3) Liver transplantation or qualification for liver transplantation, defined as a Model for End-stage Liver Disease (MELD) score  $\geq 15$  on at least 2 consecutive occasions at least 4 weeks apart
- 4) All-cause mortality

Subjects who experience a confirmed hepatic clinical event prior to completing the Week 240 Visit of the Randomized Phase will be offered the option to rollover into an Open-Label (OL) Phase of the study. Each of the clinical events (except histologic progression to cirrhosis, all-cause mortality and liver transplantation) will require confirmation by a Hepatic Events Adjudication Committee. All deaths will be reviewed by this committee to determine if they are liver-related.

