### **3.3. Adjudication Committees**

#### **3.3.1. Hepatic Events Adjudication Committee**

A key primary objective of this study is to prevent progression to cirrhosis and associated complications. A composite of clinical events that constitute the clinical efficacy endpoint have been identified and include:

- 1) Progression to cirrhosis as defined by a liver biopsy showing F4 fibrosis according to the NASH CRN classification, as assessed by the central reader.
- 2) Events of hepatic decompensation including:
  - a) Clinically apparent ascites requiring treatment
  - b) HE of Grade 2 or above (according to the West Haven criteria defined in [Appendix 5](#)) requiring treatment
  - c) Portal hypertension-related upper gastrointestinal bleeding identified by endoscopy and requiring hospitalization, including events of bleeding from esophageal varices, gastric varices, and portal hypertensive gastropathy
- 3) Liver transplantation or qualification for liver transplantation, defined as MELD score  $\geq 15$  on at least 2 consecutive occasions at least 4 weeks apart
- 4) All-cause mortality

Each of the clinical events (except histologic progression to cirrhosis, all-cause mortality and liver transplantation) will require confirmation by a Hepatic Events Adjudication Committee. All deaths will be reviewed by this committee to determine if they are liver-related. Subjects who experience one of these confirmed clinical events prior to completing the Week 240 Visit of the Randomized Phase will be offered the option to rollover into an Open-Label (OL) Phase of the study. The committee will also review all cases of HCC in the Randomized Phase as an event of special interest.

If there is clinical evidence that a subject has progressed to cirrhosis (e.g., based on the presence of new esophageal varices, changes in biomarkers [including, but not limited to, low serum albumin, high serum bilirubin, a low platelet count, prolonged INR, or elevated liver stiffness], or development of other clinical signs or symptoms of cirrhosis), the subject should undergo repeat liver biopsy for confirmation of progression to cirrhosis (F4 fibrosis as assessed by the central reader according to the NASH CRN classification) at the discretion of the primary investigator (PI).

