### 4.2. Inclusion Criteria

Subjects must meet all of the following inclusion criteria to be eligible for participation in this study.

- 1) Willing and able to give informed consent prior to any study specific procedures being performed
- 2) Liver biopsy consistent with NASH (defined as the presence of at least grade 1 steatosis, hepatocellular ballooning, and lobular inflammation according to the NAFLD Activity Score [NAS]) and bridging (F3 fibrosis) according to the NASH CRN classification, in the opinion of the central reader
  - a) A historical liver biopsy within 6 months of the Screening visit may be accepted as the Screening biopsy if the sample is deemed acceptable for interpretation by the central reader
  - b) If the subject is deemed ineligible for this study, the liver biopsy, if performed according to protocol specifications and is within 12 months of the Screening visit, may be used to determine eligibility for study GS-US-384-1944
- 3) Subject has the following laboratory parameters at the Screening visit, as determined by the central laboratory:
  - a)  $ALT \leq 8 \times ULN$
  - b)  $CL_{cr} \geq 30 \text{ mL/min}$ , as calculated by the Cockcroft-Gault equation
  - c)  $HbA1c \leq 9.5\%$  (or serum fructosamine  $\leq 381 \mu\text{mol}$  if HbA1c is unable to be resultd)
  - d) Total bilirubin  $\leq 1.3 \times ULN$  (unless an alternate etiology such as Gilbert's syndrome or hemolytic anemia is present)
  - e)  $INR \leq 1.4$ , unless due to therapeutic anti-coagulation
  - f) Platelet count  $\geq 100,000/\mu\text{L}$
- 4) Body Mass Index (BMI)  $\geq 18 \text{ kg/m}^2$  at Screening

- 5) Males and non-pregnant, non-lactating females between 18-70 years of age; inclusive based on the date of the Screening visit
- 6) Females of childbearing potential (as defined in [Appendix 3](#)) must have a negative pregnancy test at Screening and Day 1
- 7) Male subjects and female subjects of childbearing potential who engage in heterosexual intercourse must agree to use protocol specified method(s) of contraception as described in [Appendix 3](#)

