#### 4.3. Exclusion Criteria

Subjects who meet *any* of the following exclusion criteria are not to be enrolled in this study.

- 1) Prior history of decompensated liver disease, including clinical ascites, HE, or variceal bleeding
- 2) CP score > 6, as determined at Screening, unless due to therapeutic anti-coagulation
- 3) MELD score > 12, as determined at Screening, unless due to therapeutic anti-coagulation
- 4) Chronic HBV infection (HBsAg positive)
- 5) Chronic HCV infection (HCV Ab and HCV RNA positive). Subjects cured of HCV infection less than 5 years prior to the Screening visit are not eligible
- 6) Other causes of liver disease including, but not limited to, alcoholic liver disease, hepatitis B, hepatitis C, autoimmune disorders (e.g., primary biliary cholangitis, primary sclerosing cholangitis, and autoimmune hepatitis), drug-induced hepatotoxicity, Wilson disease, iron overload, and alpha-1-antitrypsin deficiency, based on medical history and/or centralized review of liver histology
- 7) History of liver transplantation
- 8) Current or history of HCC
- 9) Any weight reduction surgery in the 2 years prior to Screening or planned during the study (weight reduction surgery is disallowed during the study), and malabsorptive weight loss surgery (e.g., Roux-en-Y or distal gastric bypass) at any time prior to Screening
- 10) Weight loss > 10% within 6 months of Screening
- 11) HIV infection (HIV Ab and HIV ribonucleic acid [HIV RNA] positive)
- 12) Current alcohol consumption greater than 21 oz/week for males or 14 oz/week for females (1oz/30mL of alcohol is present in 1 12oz/360mL beer, 1 4oz/120mL glass of wine, and a 1 oz/30 mL measure of 40 proof alcohol)

- 13) Positive urine drug screen for amphetamines, cocaine or opiates (i.e. heroin, morphine) at Screening. Subjects on stable methadone or buprenorphine maintenance treatment for at least 6 months prior to Screening may be included in the study. Subjects with a positive urine drug screen due to prescription opioid-based medication are eligible if the prescription and diagnosis are reviewed and approved by the investigator
- 14) Unstable cardiovascular disease as defined by any of the following:
  - a) Unstable angina, myocardial infarction, coronary artery bypass graft surgery or coronary angioplasty within 6 months prior to Screening
  - b) Transient ischemic attack or cerebrovascular accident within 6 months prior to Screening

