**Table 5-1. List of Disallowed and Use with Caution Medicationsa**

Agents Disallowed	
Drug Class	Medications Disallowed 2 weeks prior to Day 1 through the end of treatment
Anticonvulsants b	phenobarbital, phenytoin, carbamazepine
Antimycobacterials b	rifampin, rifabutin, rifapentine c
Herbal/Natural Supplements b	St. John's Wort, Echinacea
Drug Class	Medications Disallowed 30 days prior to Day 1 through the end of treatment
Select chronic immunosuppressants	Chronic systemic d - corticosteroids, tacrolimus, sirolimus, cyclosporine, mycophenolate mofetil, and methotrexate
Farnesoid X receptor (FXR) agonists, Peroxisome Proliferator-Activated Receptor (PPAR) agonists, Chemokine Receptor (CCR) 2/5 inhibitors	obeticholic acid e , elafibranor e , and cenicriviroc e
Agents to be used with Caution	
Drug Class	Agents to be used with Caution from 30 days prior to Day 1 through end of treatment
Cardiac Medications e	digoxin f , ranolazine c , dabigatran etexilate, aliskiren

- a Not all of these example medications may be approved in each of the countries where the study is being conducted; please refer to local product information
- b May result in a decrease in the concentration of SEL
- c Not approved in Japan
- d Intra-articular, topical, nasal, epidural or inhaled routes are allowed. Chronic systemic use of corticosteroids equivalent to prednisone > 10mg/day for > 2 weeks is not allowed.
- e SEL may increase the exposure of these medications
- f For subjects on digoxin at start of study: obtain digoxin level prior to starting study drug and at the Week 1 Visit with digoxin level checks during the study period per investigator discretion. Monitor and adjust digoxin dose as necessary based on prescribing information.

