Hypomagnesemia	<LLN - 1.2 mg/dL; <LLN - 0.5 mmol/L	<1.2 - 0.9 mg/dL; <0.5 - 0.4 mmol/L	<0.9 - 0.7 mg/dL; <0.4 - 0.3 mmol/L	<0.7 mg/dL; <0.3 mmol/L; life-threatening consequences	Death
Hyponatremia	<LLN - 130 mmol/L	125-129 mmol/L and asymptomatic	125-129 mmol/L symptomatic; 120-124 mmol/L regardless of symptoms	<120 mmol/L; life-threatening consequences	Death

* Since anticoagulation medication is **NOT** captured in lab data, the condition for anticoagulation medication is ignored in the grade derivation.

a Note: Refer to Common Terminology Criteria for Adverse Events (CTCAE) Version 5.0, which can be found at https://evs.nci.nih.gov/ftp1/CTCAE/CTCAE_5.0

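### The MELD component of event-free survival has no anticoagulation exemption, although the eligibility limits on INR, Child-Pugh and MELD do, and the adjudication committee is given no rule for such cases

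*SAP*

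**What the plan says.** The third EFS component is liver transplantation or qualification for it. The definition appears in three places:

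- SAP 6.2.1: "defined as MELD score ≥ 15 on at least 2 consecutive occasions at least 4 weeks apart".
- Protocol synopsis, Randomized Study Phase: "qualification for liver transplantation, defined as a Model for End-stage Liver Disease (MELD) score" of 15 or more, on the same repeat condition.
- Protocol 3.3.1: the same threshold, "on at least 2 consecutive occasions at least 4 weeks apart".

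None of them mentions anticoagulation or a change from the subject's own baseline.

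Other parts of the plan do allow for anticoagulation:

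- Protocol 4.3 excludes "MELD score > 12, as determined at Screening, unless due to therapeutic anti-coagulation", and the Child-Pugh exclusion carries the same waiver.
- Protocol 4.2 requires INR of 1.4 or less "unless due to therapeutic anti-coagulation". No cap applies once a waiver is used.
- SAP 7.2.3 excepts anticoagulated subjects from its INR-based criteria for holding study drug.
- Protocol Table 5-1 disallows no anticoagulant. Its caution list includes "dabigatran etexilate, aliskiren", the first of which is one.

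The MELD formula (Protocol 6.11.5; SAP Appendix 4) adjusts INR only by a floor of 1.0.

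Under SAP 6.2.1 each event "will require confirmation by a Hepatic Events Adjudication Committee", apart from F4 on biopsy, death and transplantation. Under Protocol 3.3.1 a subject with a confirmed event leaves the Randomized Phase and is offered open-label selonsertib 18 mg.

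**The concern.** The same score is excused at entry when anticoagulation explains it, but not when it serves as an endpoint. A subject admitted under the waiver may be close to the endpoint threshold on Day 1, or already past it, with no liver dysfunction behind the number.

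If such a case is confirmed, EFS gains an early event that treatment cannot influence. Under blinding these events should fall in proportion to arm size, so they pull the hazard ratio towards 1. The subject also stops contributing randomized follow-up and may move to active drug, including from placebo. The two planned EFS sensitivity analyses (SAP 6.2.3) vary which deaths count and how censoring is treated, so neither would expose the problem.

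**Working it through.** **1. The plan's own power figure.** Inputs from SAP 1.3: EFS at 240 weeks 70% on placebo, hazard ratio (HR) 0.50, 20% dropout, 320 versus 160 subjects, two-sided 0.025. Take exponential event and dropout times, with rates as cumulative hazards over 240 weeks:

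- placebo events: −ln 0.70 = 0.3567
- SEL events: half of that, 0.1783
- dropout: −ln 0.80 = 0.2231

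P(event) = λ/(λ+d) × [1 − exp(−(λ+d))]

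- Placebo: 0.3567/0.5798 × (1 − 0.560) = 0.2707; × 160 = 43.3 events.
- SEL: 0.1783/0.4015 × (1 − 0.6693) = 0.1469; × 320 = 47.0 events.
- Total: 90.3 events.

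A simulated unstratified log-rank test on these inputs (40,000 trials, Monte Carlo error about 0.2 points) has power 85.2%. This agrees with the stated 85%.

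**2. What INR gives MELD 15?** From SAP Appendix 4:

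MELD = 3.78 ln(bilirubin) + 11.2 ln(INR) + 9.57 ln(creatinine) + 6.43

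With bilirubin at or below 1.0 mg/dL the first term is zero. Setting MELD to 15:

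INR = exp[(8.57 − 9.57 ln creatinine)/11.2]

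| Creatinine (mg/dL) | INR at which MELD = 15 |
|---|---|
| ≤ 1.0 | 2.15 |
| 1.1 | 1.98 |
| 1.2 | 1.84 |

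With creatinine at or below 1.0:

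| INR | 1.4 | 2.0 | 2.5 | 3.0 |
|---|---|---|---|---|
| MELD | 10.2 | 14.2 | 16.7 | 18.7 |

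At the ordinary INR entry limit of 1.4 the score is well short of 15. The MELD entry limit of 12 is passed at INR exp(5.57/11.2) = 1.64. A subject who needs the MELD waiver through INR alone is therefore at most 3 points below the endpoint threshold. The documents state no rounding of the final score; rounding to whole numbers would lower 2.15 to 2.06.

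**3. Timing.** MELD is assessed on Day 1, at Week 1 and at Week 4 (Protocol 6.3.1, 6.4.1, 6.4.2). A subject at 15 or more throughout could meet the written criterion by Week 4.

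**4. Does confirmation apply?** The exception in SAP 6.2.1 names liver transplantation, and component 3 combines transplantation with qualification for it. Protocol 6.11.5 settles the point: MELD is monitored for events that need adjudication. So the committee does see these cases. Neither document gives it criteria for them.

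**5. Size, as scenarios.** The documents give neither the fraction anticoagulated nor any INR distribution. Assume that a fraction f of each arm meets the criterion through anticoagulation, with event times uniform over Weeks 8 to 24.

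| f | Share confirmed | Power | Mean events |
|---|---|---|---|
| 0 | – | 85.2% | 90.3 |
| 0.5% | all | 83.9% | 92.2 |
| 1% | all | 82.5% | 94.1 |
| 2% | all | 80.6% | 97.9 |
| 1% | half | 84.1% | 92.2 |
| 2% | half | 82.6% | 94.1 |

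Expected false events at f = 1%, allowing for prior events and dropout to the mid-point at Week 16:

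- SEL: 3.2 × exp(−0.4015 × 16/240) = 3.12
- Placebo: 1.6 × exp(−0.5798 × 16/240) = 1.54
- Total: about 4.7, or 4.9% of 94.1 events. At 2% the total is about 9.3, or 9.5% of 97.9.

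Placing all false events at Week 4 instead (4,000 trials per scenario) gives 84.7%, 82.9% and 80.5% at f = 0, 1% and 2%. The timing assumption therefore matters little.

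**The case against.** The strongest reply is that the harm requires a committee decision the documents do not show. F4 on biopsy, death and transplantation need no confirmation, but the MELD criterion does, even though it is only a number. That suggests the committee is meant to judge whether the number represents real qualification for transplantation, and hepatologists may well reject an INR raised by anticoagulation. A charter, not available here, may say so. This stands as a reason to expect less harm. It does not remove the gap: the written definition, applied as it reads, makes stable anticoagulation an event, and rejecting the case means departing from that text.

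Committee confirmation is also not the only safeguard. With visits at most four weeks apart up to Week 48, any intervening score below 15 breaks the run. That screens out transient rises but not stable anticoagulation.

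A reader might infer more from two citations than they carry. The SAP Appendix 2 note that "the condition for anticoagulation medication is ignored in the grade derivation" concerns CTCAE grading from laboratory files. It does not mean adjudicators cannot see anticoagulant use, because Protocol 5.4 has all concomitant medication recorded. And dabigatran is on the caution list because selonsertib may raise its exposure. The listing shows that anticoagulants are allowed, not that such MELD values occur.

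The blinded data in Protocol 1.2.10.1 show no sign of a problem: 425 treated, 3 discontinued and 421 continuing leave one subject unaccounted for. In the sister study (Protocol 1.2.11.2), at a similar median exposure, six subjects with events had already moved to open label. This is mild evidence against a large effect. It sets no bound, because adjudication takes time and rollover may follow up to 60 days after confirmation.

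**Conclusion.** The inconsistency is real: anticoagulation is exempted at entry and in the drug-hold criteria, but not in EFS component 3, and the committee has no written rule for it. This is a low-cost improvement to the definition, not a demonstrated flaw in the result.

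Three stronger readings should be resisted:

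- **That the EFS test is biased towards selonsertib.** The false events would be non-differential under blinding. They cost power and do not inflate type I error.
- **That the 85% power is wrong.** It is reproduced on the plan's own assumptions.
- **That power will fall to about 83% or 81%.** Those figures apply if 1% or 2% of each arm has a *confirmed* false event. That fraction is narrower than the anticoagulated fraction: INR must stay at about 1.8 to 2.15 or above (for creatinine 1.2 down to 1.0) across consecutive visits, and the committee must accept the case. If it rejects every one, nothing is lost.

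**What to change.** In SAP 6.2.1 and in the adjudication instructions, add "unless due to therapeutic anti-coagulation" to the MELD criterion. The blinded committee would apply it from the recorded concomitant medications, and would still confirm a case in an anticoagulated subject when bilirubin or creatinine drives the rise. Until the protocol matches, list the difference in SAP 6.5. Carry the wording into the synopsis and Protocol 3.3.1 at the next amendment. If a charter already contains such a rule, citing it in the SAP is enough.

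The SAP and committee changes are cheap and use data already collected, but they should be made before unblinding. The protocol text costs more: Protocol 9.2.1 requires ethics approval of modifications, and about 460 centers are planned, so this point alone does not justify an amendment. The statistical price is an added attribution judgement and the possible loss of some true INR-driven deterioration in anticoagulated subjects, which would then have to be caught by another EFS component or by the committee.
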